4.2 Exclusion Criteria

4.2.1 Breastfeeding, pregnancy, or plans to become pregnant.

4.2.2 Known allergy/sensitivity or any hypersensitivity to components of the study drugs, or their formulations.

4.2.3 Presence of any confirmed or probable active TB based on criteria listed in the current ACTG Diagnosis Appendix at screening.

4.2.4 History of rifamycin-monoresistant, INH-monoresistant, multi-drug resistant (MDR), or extensively-drug resistant (XDR) TB at any time prior to study entry.

- 4.2.5 Known exposure to rifamycin-monoresistant, INH-monoresistant, MDR- or XDR-TB (e.g., household member of a person with rifamycin-monoresistant, INH-monoresistant, MDR- or XDR-TB) at any time prior to study entry by participant self report or medical records.
- 4.2.6 **History** of peripheral neuropathy Grade ≥ 2 according to the Division of AIDS Table for Grading the Severity of Adult and Pediatric Adverse Events (DAIDS AE Grading Table), Corrected Version 2.1, July 2017, which can be found on the DAIDS RSC website at <https://rsc.niaid.nih.gov/clinical-research-sites/daids-adverse-event-grading-tables>.
- 4.2.7 Active drug or alcohol use or dependence that, in the opinion of the site investigator, would interfere with adherence to study requirements.
- 4.2.8 Acute or serious illness requiring systemic treatment and/or hospitalization within 7 days prior to study entry.
- 4.2.9 Known cirrhosis, a history of decompensated liver disease (ascites, hepatic encephalopathy, or esophageal varices) or current Child Pugh Class B or C hepatic impairment.

NOTE: Refer to [section 6.3.10](#) for Child Pugh scoring and classification table.

- 4.2.10 Initiated, discontinued, or changed doses of drugs that are P-glycoprotein (PGP) inducers, that are P-glycoprotein (PGP) inhibitors, or that are known to have drug interactions with DTG, within 30 days prior to study entry.

NOTE: Refer to the list of prohibited and precautionary medications in [Appendix I](#).

- 4.2.11 Known porphyria at any time prior to study entry.
- 4.2.12 Receipt of any other antiretroviral therapy other than DTG and 2 NRTI within 28 days prior to study entry.
- 4.2.13 Receipt of TAF within 28 days prior to study entry.

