For additional information on the protocol registration process and specific documents required for initial and amendment registrations, refer to the current version of the DAIDS Protocol Registration Manual.

Once a candidate for study entry has been identified, details will be carefully discussed with the participant. The participant (or, when necessary, the legal representative if the participant is under guardianship) will be asked to read and sign the approved protocol consent form.

Participants from whom a signed informed consent has been obtained may be screened and enrolled, if they otherwise qualify. An ACTG Screening Checklist must be entered through the DMC Participant Enrollment System.

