4.3.3 Participant Registration

For participants from whom informed consent has been obtained, but who are deemed ineligible or who do not enroll into the initial protocol step, an ACTG Screening Failure Results form must be completed and keyed into the database.

Participants who meet the enrollment criteria will be registered to the study according to standard ACTG DMC procedures.

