7.4 Study Monitoring

The core team will monitor the conduct and safety of the study via regular summaries of accrual, study discontinuation (to ensure the total target number of evaluable participants is met), stored sample completeness (to ensure that samples for primary and secondary outcome measures are collected as expected), and adverse events. An evaluable participant will be considered any participant who has completed the 28 daily doses of RPT/INH within the 6 week time period from study entry and has additionally completed both intensive PK visits with a minimum of 6 samples collected at each PK visit. The 23- and 24-hour (trough) time points must be part of the 6 collected samples.

The site should notify the core team within 72 hours (preferably within 48 hours) by email if a participant has not completed each of the two intensive PK visits with at least 6 plasma sample collections including the 23- and 24-hr PK draws, or if a participant has not completed 28 daily doses of RPT/INH within the 6-week time period from study entry.

During the study, the safety and tolerability of the study medication will be monitored by toxicity reports presenting laboratory and clinical data. The core team will discuss these reports on regularly-scheduled conference calls or by e-mail. It is the responsibility of the core team to interpret the toxicity data and make any decisions needed to protect participants from undue risk. Any concerns will be presented to the DAIDS Clinical Representative.

The DAIDS clinical representative will review and assess EAE reports for potential impact on the study participant safety and protocol conduct as per DAIDS policies, guidance documents, and SOPs, as applicable. Additionally, the DAIDS clinical representative will review aggregated adverse event summaries by arm prepared quarterly by the SDAC.

The study will undergo interim feasibility and safety review approximately every 6 months after the enrollment of the first participant by an ACTG-appointed Study Monitoring Committee (SMC). The first interim review will occur no more than 6 months after the enrollment of the first study participant.

An SMC interim review may also be convened if a concern is identified by the DAIDS clinical representative, the study chairs, or study statistician in consultation with the CMC team. See [section 10.0](#) for statistical and other considerations related to interim monitoring.

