chemistries repeated until resolution to <ULN or to baseline if abnormal at entry, as above. Reintroduce the study-supplied drug(s) with caution. **Locally provided DTG should be discontinued if suspected in the site investigator's causality assessment.**

INH, RPT, and study-supplied DTG will be permanently discontinued in the event of Grade 3 to 4 AST (SGOT), ALT (SGPT) (≥ 5 ULN) or total bilirubin ($\geq 2.6 \times$ ULN) toxicity that is definitely, probably, or possibly related to study-supplied drugs. **Locally provided DTG should be discontinued if suspected in the site investigator's causality assessment.** Premature treatment discontinuation evaluations should be completed. The participant should be followed until the AE has decreased to Grade ≤ 2 . After the AE has decreased to Grade ≤ 2 , premature study discontinuation evaluations should be completed, and then the participant will be taken off study. ART management will be at the discretion of the site investigator.

In consultation with the team, careful assessments should be done to rule out the use of alcohol, non-study medication-related toxicity, or viral hepatitis (including viral hepatitis complicated by immune reconstitution inflammatory syndrome) as the cause for any liver toxicity that warrants permanent study drug discontinuation based on the liver stopping criteria specified above. Specific tests that may be considered are listed on the PSWP.

Peripheral Neuropathy

Peripheral neuropathy associated with INH is usually avoided by the concurrent administration of pyridoxine (vitamin B6). In this study, all participants will take vitamin B6 concomitantly with INH. If peripheral neuropathy develops, every effort should be made to determine the etiology (i.e., whether the neuropathy is due to INH toxicity, alcohol, or other factors). Participants with peripheral neuropathy Grade ≤ 2 may be entered into the study, but should be monitored carefully for any progression of peripheral neuropathy.

For Grade 1 or 2, continue study-supplied drugs and follow the participant more frequently for progression of peripheral neuropathy. Consider increase in vitamin B6 dose.

For Grade 3 or 4, study-supplied drugs must be permanently discontinued, **as well as any other drugs suspected in the site investigator's causality assessment.**

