4.2.1 Primary PK Analysis Population

Primary PK Analysis Population (separately defined for Arm 1 and Arm 2 participants): The primary PK analysis population consists of those participants who: (1) met all study entry criteria, (2) initiated the 1HP TB regimen and completed 28 daily doses RPT/INH within the 6-week study period, and (3) took DTG twice-daily (Arm 1) or once-daily (Arm 2) for days 1-28 (that is, for the participant, both PK profiles are available (before initiating 1HP and while taking 1HP).

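### Protocol 8.4 says a candidate with current Grade 2 peripheral neuropathy may be entered, while exclusion 4.2.6 bars that candidate (minor)

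*Protocol*

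**What the plan says.** Three statements in the protocol bear on this. The grade limits are given in words here because inequality signs can be altered when a PDF is read by a program.

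- **Protocol 4.2.6 (exclusion).** A candidate is excluded for a history "of peripheral neuropathy Grade" 2 or higher on the DAIDS grading table. No time window is attached.
- **Protocol 8.4, Peripheral Neuropathy (entry sentence).** "Participants with peripheral neuropathy Grade" 2 or lower "may be entered into the study, but should be monitored carefully for any progression of peripheral neuropathy".
- **Protocol 8.4, next paragraph (on-study rule).** "For Grade 1 or 2, continue study-supplied drugs and follow the participant more frequently for progression of peripheral neuropathy". Grade 3 or 4 requires permanent discontinuation of study-supplied drugs.

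On enrolment itself, Protocol 4.3.1 says consented candidates "may be screened and enrolled, if they otherwise qualify", and 4.3.3 says "Participants who meet the enrollment criteria will be registered to the study". Section 6.2.2 places the Day 0 evaluations after eligibility has been determined from screening.

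**The concern.** An eligibility statement appears in the toxicity section and does not match the exclusion list. At Grade 2 the two limits overlap: one rule includes Grade 2 among those who may enter, and the other includes it among those who may not.

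Isoniazid-associated neuropathy is a risk that 8.4 itself names, and 4.2.6 has an evident safety purpose in a regimen of 300 mg isoniazid daily. An investigator facing a candidate with neuropathy might reasonably open the neuropathy paragraph for guidance. That paragraph would say that Grade 2 is acceptable with monitoring. Enrolment on that basis would be an eligibility violation in a person with existing nerve damage.

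The paragraph also speaks only of grade, without mentioning history. A reader who stops there gets no prompt to ask about an earlier and worse episode.

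**Working it through.** No arithmetic applies. The check applies each rule to each type of candidate.

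**Inputs.** The entry sentence in 8.4 (Grade 2 or lower may enter). Exclusion 4.2.6 (history of Grade 2 or higher barred, no time limit). The separate on-study rule in 8.4.

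**Step 1. Is the 8.4 sentence about entry at all?** It speaks of being entered into the study, and the paragraph after it deals separately with Grade 1 or 2 neuropathy in people on study drugs. If the first sentence were also an on-study rule, its reference to entry would have no meaning. It is an entry statement.

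**Step 2. Does a history of Grade 2 include a current Grade 2?** It should. Otherwise 4.2.6 would bar a resolved Grade 2 episode and leave an active one unaddressed, which cannot be the purpose of a safety exclusion.

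**Step 3. Compare the rules.**

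| Candidate at screening | 8.4 entry sentence | Exclusion 4.2.6 | Result |
|---|---|---|---|
| Current Grade 1, never worse | May enter | Not barred | Agree |
| Current Grade 2 | May enter | Barred | **Contradict** |
| Current Grade 3 or 4 | No permission given | Barred | Agree |
| Current Grade 1, past Grade 2 or higher | Does not address past grade | Barred | 4.2.6 stands alone; 8.4 gives no reminder |

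**Step 4. Is there a reconciling sentence?** Sections 4.3.1, 4.3.3 and 6.2.2 tie registration to the enrolment criteria. None of them refers to 8.4, and 8.4 does not refer to 4.2.6.

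**The case against.** The strongest reply is that 8.4 admits nobody. Its wording is permissive and it sits among toxicity-management rules. Eligibility requires every criterion in Section 4 to be met, and registration depends on those criteria. Sites also work from a screening checklist (4.3.1). A breach would need a site to set the exclusion list aside in favour of a toxicity paragraph. The safety stakes are limited too: pyridoxine accompanies every isoniazid dose, the course is 28 doses, and 8.4 continues study drugs when Grade 2 neuropathy arises on study.

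Most of this stands, and it is why the point is minor. Section 4 would normally control. But that resolves the contradiction only for a reader who notices it. The protocol still states two incompatible answers for current Grade 2.

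A second reply is that the conflict depends on one inequality sign. That is correct: if the PDF of 8.4 says strictly below Grade 2, the contradiction disappears. Nothing in the available text suggests that the sign was altered.

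A reader might also infer that the rules contradict each other for someone now at Grade 1 with a worse past. The text does not support that. Section 8.4 is silent on past grade, so 4.2.6 bars that person without opposition. The missing reminder is a weakness in the wording, not a conflict.

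**Conclusion.** The 8.4 entry sentence is wrong as written. It contradicts exclusion 4.2.6 for one type of candidate, the person with current Grade 2 neuropathy, and it omits any reminder that a past episode of Grade 2 or higher excludes. This is a minor internal inconsistency. The documents give no count of candidates with neuropathy, so the number affected cannot be estimated.

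The conclusion rests on two assumptions: that the inequality signs were read correctly from the PDF, and that a current grade counts as part of a candidate's history.

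A reader might go further and infer that the sentence threatens the PK analysis. SAP 4.2.1 requires that primary PK participants "1) met all study entry criteria", whereas Protocol 7.4 defines evaluability by doses and samples: "An evaluable participant will be considered any participant who has completed the 28 daily doses of RPT/INH" in the allowed time, with the required PK samples. A wrongly enrolled participant could satisfy the second definition and fail the first. That mismatch would arise from any eligibility breach, whatever 8.4 said, so it does not add to the weight of this point. The sample size and the planned primary PK analysis are unaffected.

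**What to change.** Either of two edits to Protocol 8.4 is enough:

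- delete the entry sentence and refer the reader to 4.2.6; or
- replace it with: *Participants with Grade 1 peripheral neuropathy and no history of Grade 2 or higher (see 4.2.6) may be entered, and should be monitored carefully for progression.*

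The first is cleaner because eligibility then appears in one place only. The second keeps the monitoring advice and supplies the missing reminder about past episodes. In both cases the on-study rule for Grade 1 or 2 stays unchanged.

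The cost is one sentence in a clarification memo or the next amendment. Design, sample size and data collection do not change.

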8.5 Pregnancy Outcomes and Reporting

Pregnant women must discontinue study medication and study evaluations, but will be encouraged to remain on study to collect pregnancy outcome data. The outcome and the adverse events for the participant and infant will be recorded on an outcome eCRF.

Pregnancies that occur on study should be reported prospectively to The Antiretroviral Pregnancy Registry. More information is available at www.apregistry.com. [contact]; [contact]. (For studies conducted at sites outside the United States, report to The Antiretroviral Pregnancy Registry—[contact]; [contact] or [contact].)

9.0 CRITERIA FOR DISCONTINUATION

9.1 Permanent and Premature Treatment Discontinuation

- Pregnancy
- Drug-related toxicity (see sections [8.1](#), [8.2](#), [8.3](#), and [8.4](#))
- At the discretion of the ACTG, IRB/EC, FDA, NIAID, Office for Human Research Protections (OHRP), other government agencies as part of their duties, investigator, or industry supporter

9.2 Premature Study Discontinuation

- Request by the participant to withdraw
- Requirement for prohibited concomitant medications (see section [5.5](#))
- Clinical reasons believed life-threatening by the physician, even if not addressed in the [toxicity section](#) of the protocol
- Failure by the participant to complete either of the intensive PK visits
- Participant repeatedly noncompliant (per investigator's discretion) with study medications as prescribed
- Request of the primary care provider if she or he thinks the study is no longer in the best interest of the participant
- At the discretion of the ACTG, IRB/EC, FDA, NIAID, Office for Human Research Protections (OHRP), other government agencies as part of their duties, investigator, or industry supporter

10.0 STATISTICAL CONSIDERATIONS

10.1 General Design Issues

This is an open-label, two-arm, multicenter PK study to examine drug-drug interactions between RPT and DTG in HIV-1 and LTBI co-infected participants.

Participants in Arm 1 will receive DTG 50 mg BID in combination with 1HP for 4 weeks. After 36 participants from Arm 1 are enrolled and PK data are available, a review of DTG trough concentrations by the team and the SMC will take place to determine whether Arm 2 should open based on an analysis of DTG trough concentrations. There will be a pause in study enrollment between the completion of Arm 1 and the start of Arm 2.

If the team decides to open Arm 2, participants in Arm 2 will receive DTG 50 mg QD in combination with 1HP for 4 weeks.

Participants will serve as their own controls and PK parameters of DTG will be compared in the presence or absence of 1HP. The maximum sample size is 72 participants.

10.2 Outcome Measures

Primary and secondary outcome measures listed below will be addressed in the study's primary Statistical Analysis Plan, which will define the content of the Primary Analysis Report. This report will form the basis for the primary study manuscript and results reporting to ClinicalTrials.gov. Outcomes of interest for secondary and exploratory objectives intended for subsequent publications listed under "Other Outcome Measures".

10.2.1 Primary Outcome Measures

Evaluation of effect of 1HP on the PK of DTG in plasma

- 10.2.1.1 Plasma DTG PK parameters (C_{max} , area-under-the-curve (AUC₀₋₁₂ for BID & AUC₀₋₂₄ for QD dosing), C_{min}) at Day 0 and Day 28 (-2/+14 days), by arm.
- 10.2.1.2 Plasma DTG PK parameter (C_{trough}) at Day 28 (-2/+14 days), by arm.

10.2.2 Secondary Outcome Measures

- 10.2.2.1 Proportion of participants with all adverse events meeting the reporting criteria in [Section 7.2](#) during administration of DTG with 1HP, by arm.
- 10.2.2.2 Proportion of participants who discontinue study or study drugs during DTG and 1HP dosing, by arm.
- 10.2.2.3 Proportion of participants with HIV-1 RNA levels >50 copies/mL at Day 28 (-2/+14 days) and/or at the Follow Up visit.

10.2.3 Other Outcome Measures

Model predicted dosing of DTG during concomitant 1HP

10.2.3.1 Dosing algorithm for DTG in the presence of RPT/INH dosing derived by simulation using nonlinear mixed effects models.

Evaluation of the role of pharmacogenomics on DTG and RPT PK

10.2.3.2 PK parameters of DTG in the presence or absence of 1HP, taking into account relevant pharmacogenetics (SNPs TBD).

10.2.3.3 PK parameters of RPT after 1HP dosing taking into account relevant pharmacogenetics (SNPs TBD).

Combined evaluation of DTG and RPT PK models

10.2.3.4 Joint pharmacokinetic model of RPT and DTG PK and its DDI where relationship and interaction between dynamic RPT and DTG concentrations is modelled, quantified and described.

10.3 Randomization and Stratification

Participants will be enrolled into the study without randomization since the accrual for Arm 1 will be completed when the decision to open Arm 2 will be made.

10.4 Sample Size and Accrual

Sample size estimates are aimed to provide data to support precise estimation of the pharmacokinetic model parameters for DTG in the presence and absence of 1HP. These models, once validated, will further be used to deliver dosing algorithms for DTG to be recommended for treatment of patients living with HIV and co-infected with LTBI, pending appropriate safety assessment.

The sample size assessment was done by evaluating different study designs (varying number of participants and time points) using clinical trial simulations. The stochastic simulation-estimation (SSE) methodology for clinical trial simulation and re-estimation was employed to evaluate sample sizes required to evaluate key pharmacokinetic parameters with precision adequate for decision making on use of RPT + DTG at the proposed doses. This methodology simulates the data from the planned trial with proposed design (number of samples, participants) followed by the estimation of the parameters under the true and alternative models. This is repeated at least 1000 times and parameter estimates relative standard errors and between subject variability (BSV) estimates are assessed. This methodology was used to assess sample size calculations and probability of opening Arm 2. The effect of RPT on DTG PK parameters

(bioavailability) was assumed to be 30%-50% decrease based on a previously developed model of DTG + 3HP [16]. The range of inter-participant variability in PK parameters (CL and F) was assumed to be 25-40%. The team has assumed design where each participant is its own control and time course of RPT induction is considered. Under these assumptions, data from ≥ 32 participants will provide $>80\%$ power to detect the DDI effect on bioavailability and to unbiasedly (relative bias $<5\%$) and precisely (RSE $<25\%$) estimate PK parameters and inter-participant variability. These unbiased parameters will be then used for simulations of Arm 2 and derivation of the median 5th percentile of DTG troughs by simulations. Probability of opening Arm 2 will be dependent on magnitude of both, decrease in bioavailability due to DDI and between participant variability. Decrease in bioavailability of up to 35% coupled with acceptable inter-participant variability (up to 30%) will provide 90% chance of satisfying criteria for opening Arm 2.

The proposed design for DTG requires 32 evaluable participants with at least 6 plasma sample collections which must include the 23- and 24-hr samples on each of the two intensive PK visits in order to estimate pharmacokinetic parameters with required the precision defined as relative standard errors $<10\%$ for typical values and RSE $<25\%$ for random effects (between subject variability).

To protect against loss of the primary outcomes (e.g., unevaluable PK measurements) after study accrual is closed, the study will enroll 36 participants in each arm. This is an increase of $\sim 12\%$ from the required sample size of 32 evaluable participants.

Data from participants who drop out between sampling times or participants who do not have at least 6 sample collections on each of the two intensive PK visits will be utilized in the analysis, however, those participants will not be counted towards full sample size requirement (i.e., 36 participants in each arm) and will be replaced.

10.5 Data and Safety Monitoring

10.5.1 Interim Monitoring Guidelines

The core team will monitor adverse events (AEs) on a regular basis. Should 3 or more participants experience Grade 3 or higher AEs deemed to be definitely, probably, or possibly related to DTG or RPT or INH, the study will be halted while a safety review is conducted by the ACTG's Tuberculosis Transformative Science Group (TB TSG) SMC. **The core team will also monitor viral loads on Days 28, 42, and 49 on a regular basis. Specifically, at the time of the interim review for Arm 1, the proportion of participants with HIV-1 viral load above 50 c/mL will be reported.**

